10.3.2 Definition of Serious Adverse Event

If an event is not an AE per the definition above, then it cannot be an SAE even if serious conditions are met (eg, hospitalization for signs/symptoms of the disease under study, death due to progression of disease).

A Serious Adverse Event Is Defined as Any Untoward Medical Occurrence That, at Any Dose:

 • Results in death

 • Is life-threatening The term ‘life-threatening’ in the definition of ‘serious’ refers to an event in which the participant was at risk of death at the time of the event. It does not refer to an event, which hypothetically might have caused death, if it were more severe.

 • Requires inpatient hospitalization or prolongation of existing hospitalization In general, hospitalization signifies that the participant has been detained (usually involving at least an overnight stay) at the hospital or emergency ward for observation and/or treatment that would not have been appropriate in the physician’s office or outpatient setting. Complications that occur during hospitalization are AEs. If a complication prolongs hospitalization or fulfills any other serious criteria, the event is serious. When in doubt as to whether “hospitalization” occurred or was necessary, the AE should be considered serious. Hospitalization itself should not be reported as an SAE; whenever possible the reason for the hospitalization should be reported. Hospitalizations or prolonged hospitalizations for social admissions (ie, those required for reasons of convenience or other nonmedical need) are not considered SAEs. Hospitalization for elective treatment of a pre-existing condition that did not worsen from baseline is not considered an AE.

 • Results in persistent disability/incapacity The term disability means a substantial disruption of a person’s ability to conduct normal life functions. This definition is not intended to include experiences of relatively minor medical significance such as uncomplicated headache, nausea, vomiting, diarrhea, influenza, and accidental trauma (eg, sprained ankle) which may interfere with or prevent everyday life functions but do not constitute a substantial disruption.

 • Is a congenital anomaly/birth defect

 • Other situations: Medical or scientific judgment should be exercised in deciding whether SAE reporting is appropriate in other situations such as important medical events that may not be immediately life-threatening or result in death or hospitalization but may jeopardize the participant or may require medical or surgical intervention to prevent one of the other outcomes listed in the above definition. These events should usually be considered serious. Examples of such events include invasive or malignant cancers, intensive treatment in an emergency room or at home for allergic bronchospasm, blood dyscrasias or convulsions that do not result in hospitalization, or development of drug dependency or drug abuse.

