7. DISCONTINUATION OF STUDY INTERVENTION AND PARTICIPANT DISCONTINUATION/WITHDRAWAL

7.1 Discontinuation of Study Intervention Dosing

Participants have the right to discontinue study intervention or withdraw from the study at any time for any reason. Participants may withdraw or be withdrawn from study-related procedures and intervention for the following reasons:

- Withdrawal of consent
- Adverse event
- Protocol deviation
- Investigator decision
- Pregnancy ([Appendix 4](#))
- Sponsor decision to terminate the study
- Loss to follow-up

In particular, study intervention should be discontinued if participants experience the following:

- Grade ≥ 3 infusion reaction such as severe anaphylaxis or cytokine release syndrome
- At the discretion of the Investigator, study intervention may be stopped if the participant has an unexplained decline of eGFR of $> 30\%$ sustained over 3 months that is not reversed after correction of all reversible factors such as volume depletion, NSAID, ACEI/ARB, other nephrotoxic drug use, or resolution of acute illness or infection.

All AEs should be followed until resolution or for a period of 30 days after the EOS, whichever is shorter ([Section 8.3.1](#)). If the participant withdrew because of an AE, every effort must be made to perform protocol-specified safety follow-up procedures.

If study intervention dosing is definitively discontinued, participants are encouraged to continue with assessments as per the schedule of assessments. At a minimum, if study participation is terminated by the participant or Investigator, the participant should complete all early termination assessments and will be encouraged to return for the EOS assessments outlined in [Table 1](#). The primary reason for discontinuation should be recorded in the appropriate section of the eCRF.

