8.2.4 Clinical Safety Laboratory Assessments

Clinical laboratory evaluations for safety will be performed by a central laboratory whenever possible, however, local laboratory tests may be utilized for more urgent safety monitoring. Before starting the study, the Investigator will provide the Sponsor (or its designee) copies of all laboratory certifications and normal ranges for all laboratory assessments to be performed by that laboratory. Local laboratory assessments to make intervention-related decisions may be performed at all visits.

A list of clinical safety laboratory tests to be performed is provided in Appendix 2 and the timing for these assessments is provided in [Table 1](#). All protocol-required laboratory assessments must be conducted in accordance with the laboratory manual. Details of laboratory tests to be conducted for assessment of VIS649 PK, PD, exploratory biomarkers, and immunogenicity are provided in Sections [8.5](#), [8.6](#), [8.8](#), and [8.9](#), respectively.

The Investigator must review the laboratory report, document this review, and record any clinically relevant changes occurring during the study in the AE section of the CRF. The laboratory reports must be filed with the source documents. Clinically significant abnormal laboratory findings are those which are not associated with the underlying disease, unless judged by the Investigator to be more severe than expected for the participant's condition.

All laboratory tests with values considered clinically significantly abnormal, with the exception of disease defining abnormalities such as eGFR and proteinuria considered to be a part of the natural history of IgAN, during participation in the study or within 30 days after the last dose of study intervention should be repeated until the values return to normal or baseline or are no longer considered clinically significant by the Investigator or medical monitor.

If such values do not return to normal/baseline within a period of time judged reasonable by the Investigator, the etiology should be identified, and the Sponsor notified.

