8.3.2 Method of Detecting Adverse Events and Serious Adverse Events

The method of recording, evaluating, and assessing causality of AE and SAE and the procedures for completing and transmitting SAE reports are provided in [Appendix 3](#).

Care will be taken not to introduce bias when detecting AEs and/or SAEs. Open-ended and nonleading verbal questioning of the participant is the preferred method to inquire about AE occurrences. For example, participants should be asked the nonleading question: “How have you felt since your last visit?”

Exacerbation or disease progression should be reported as an AE only if there are unusual or severe clinical features that were not present, or experienced earlier, or not expected based on the course of the condition.

In addition, the Sponsor must be notified immediately by telephone, fax, or e-mail of any immediately reportable events. Immediately reportable events (IRE) include the following:

- SAEs
- Pregnancies. Although normal pregnancy is not an AE, it will mandate study intervention discontinuation and must be reported on an IRE form and the Pregnancy Surveillance Form(s) to the Sponsor. Pregnancy will only be documented on the AE eCRF if there is an abnormality or complication. This includes pregnancy of the participant or the participant’s partner

Adverse event, start date, end date, seriousness, severity, relationship to study intervention, action taken with study treatment and outcome will be recorded on the source documents and in

the eCRF. Special attention should be paid to recording hospitalization and concomitant medications.

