
 • Any abnormal laboratory test results (hematology, clinical chemistry, or urinalysis) or other safety assessments (eg, ECG, radiological scans, vital signs measurements), including those that worsen from baseline, considered clinically significant in the medical and scientific judgment of the Investigator (ie, not related to progression of underlying disease). It is the Investigator’s responsibility to review the results of laboratory tests for each individual participant as they become available. This review will be documented by the Investigator’s dated signature on the laboratory report. The Investigator may repeat the laboratory test or request additional tests to verify the results of the original laboratory tests. • Exacerbation of a chronic or intermittent pre-existing condition including either an increase in frequency and/or intensity of the condition. • New conditions detected or diagnosed after study intervention administration even though it may have been present before the start of the study. • Signs, symptoms, or the clinical sequelae of a suspected drug-drug interaction. • Signs, symptoms, or the clinical sequelae of a suspected overdose of either study intervention or a concomitant medication. Overdose per se will not be reported as an AE/SAE unless it is an intentional overdose taken with possible suicidal/self-harming intent. Such overdoses should be reported regardless of sequelae.

Events NOT Meeting the Adverse Event Definition

 • Any clinically significant abnormal laboratory findings or other abnormal safety assessments which are associated with the underlying disease, unless judged by the Investigator to be more severe than expected for the participant’s condition. • The disease/disorder being studied or expected progression, signs, or symptoms of the disease/disorder being studied, unless more severe than expected for the participant’s condition. • Medical or surgical procedure (eg, endoscopy, appendectomy): the condition that leads to the procedure is the AE. • Situations in which an untoward medical occurrence did not occur (social and/or convenience admission to a hospital). • Anticipated day-to-day fluctuations of pre-existing disease(s) or condition(s) present or detected at the start of the study that do not worsen.

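### Hospitalizations and deaths judged to be expected IgAN progression fall outside AE/SAE reporting, with no threshold and no other event-level capture described

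*Protocol*

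**What the plan says.** **AE definition (Protocol 10.3.1).** The list of things that are not AEs includes "The disease/disorder being studied or expected progression, signs, or symptoms of the disease/disorder being studied", unless worse than expected for that participant. The list of things that are AEs includes "Exacerbation of a chronic or intermittent pre-existing condition including either an increase in frequency and/or intensity of the condition".

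**Body text (Protocol 8.3.2).** "Exacerbation or disease progression should be reported as an AE only if there are unusual or severe clinical features", and those features must be new to the participant or not expected from the course of the condition.

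**SAE definition (Protocol 10.3.2).** For an event that does not qualify as an AE, the section states: "cannot be an SAE even if serious conditions are met (eg, hospitalization for signs/symptoms of the disease under study, death due to progression". The seriousness criteria that follow begin with an event that leads to death.

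**Laboratory findings (Protocol 8.2.4).** Findings associated with the underlying disease do not count as clinically significant unless judged worse than expected. A separate clause, "with the exception of disease defining abnormalities such as eGFR and proteinuria considered to be a part of the natural history of IgAN", limits which abnormal results must be retested.

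**Kidney criterion (Protocol 7.1).** Among the grounds on which the investigator may stop study drug is an unexplained eGFR fall of more than 30% "sustained over 3 months that is not reversed after correction of all reversible factors".

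**Analysis (SAP).** The AE summary in 4.7.2 has one line for deaths, restricted to treatment-related TEAEs. Section 1.2.3 lists death among the withdrawal reasons, and 4.1 tabulates reasons for discontinuation. eGFR is analysed as change from baseline (4.4.1.3) and slope (4.4.1.4, 4.4.2). Laboratory values are summarized by visit and at last evaluation, and CTCAE shift tables are optional (4.7.3).

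**The concern.** The kidney is the target organ, so whether the drug makes kidney disease worse in some participants is a central safety question. A single case cannot answer it: a hospitalized flare on drug looks like a hospitalized flare from IgAN. Only the comparison with placebo separates the two, and that comparison needs all such events in both arms.

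Here the investigator's attribution comes first. An event called expected progression leaves the AE and SAE data before any comparison by arm is made. Protocol 2.3.2 describes IgAN as a disease with periodic flares, and 2.1 and 2.2 describe progression to end-stage disease as its natural course, so that attribution is easy to reach. With no threshold, and with sections that point in different directions, two sites could classify the same event differently.

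**Working it through.** No arithmetic applies. The check is to follow one event through the rules, then see what would record it otherwise.

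**1. A hospitalized IgAN flare judged to be expected progression.**
- 10.3.1: not an AE, because it is expected progression and is not judged worse than expected.
- 10.3.2: not an AE, so not an SAE, although hospitalization is a seriousness criterion. The event matches the section's own first example.
- Consequence: no 24-hour SAE report (8.3.1), no row in the TEAE tables (SAP 4.7.2), and no entry in the AE data that the DSMB reviews (Protocol Table 2).

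**2. The same event under the other rules.**
- 10.3.1, list of events that are AEs: a flare that is more frequent or more intense is an exacerbation of a chronic pre-existing condition, so it is an AE.
- 8.3.2: the test is unusual or severe features that are new or unexpected. An unusual feature that is not more severe could pass here and fail the exclusion test in 10.3.1, which turns on severity alone.
- A severe flare like one the participant had earlier may fail the 8.3.2 test because it is not new, yet meet the exacerbation rule in 10.3.1.
- Death from progression: 10.3.2 gives it as an example of a non-SAE, directly above a list in which death is the first criterion.

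None of these sections says how much worse than expected an event must be, or which section prevails.

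**3. Other places where the event might be recorded.**
- 8.3.2 asks for special attention to recording hospitalization. That sentence ends the paragraph on which fields to complete for an AE, so it does not clearly reach an event ruled not to be one.
- SAP 1.2.3 and 4.1 would count a death that ended participation, but without its cause. A hospitalization that did not end participation would not appear.
- SAP 4.7.2 would not show the death, since its death line requires a treatment-related TEAE.
- Protocol 9.6 leaves the content of DSMB reviews to a charter that is not among the documents.

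**4. What remains visible.**
- Clinical laboratory tests are part of the primary safety endpoint (Protocol, Section 3).
- Creatinine is required at screening, Month 0, monthly to Month 12, and Month 15 (Protocol Table 1 and its chemistry footnote).
- The DSMB assesses unblinded laboratory data (Protocol Table 2).
- All laboratory values, and all abnormal ones, are listed (SAP 4.7.3).

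Renal function values therefore reach both the safety analysis and the DSMB whatever the attribution.

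**5. Whether those summaries replace an event count.** They do so only in part. Changes and slopes are averages over arms of about 36, in which a few marked deteriorations can be hard to see. No planned table counts participants with a sustained eGFR fall of more than 30%, although 7.1 already names that figure and the monthly creatinine supports the count.

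**The case against.** The strongest case on the other side has five parts.

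**The rule is conditional.** A reader might infer that 10.3.2 bars every IgAN-related hospitalization or death from being an SAE. It does not. It applies only to events that are not AEs, and 10.3.1 and 8.3.2 both readmit worsening beyond expectation. Participants enter with eGFR of at least 45 and without T2 or C2 biopsy findings, so dialysis or death from IgAN within about 15 months would ordinarily be worse than expected. This stands as a limit on scope. It does not settle the matter, because the example of death in 10.3.2 steers the investigator the other way.

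**Renal harm is not hidden.** A reader might also infer that serious renal worsening can drop out of the primary safety data and the DSMB's view. For renal function that is wrong, for the reasons in step 4 of the working.

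**The 8.2.4 and 7.1 passages prove little here.** The natural-history clause in 8.2.4 concerns repeat testing, not AE capture. The 7.1 criterion requires an unexplained fall, so it is not automatically exempt from AE reporting. Both points stand.

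**General and specific rules can coexist.** Exacerbation of a chronic condition can be read as the general rule, with the studied disease as its exception. That is a fair reading, but the text does not say so, and the tests in 8.3.2 and 10.3.1 still differ.

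**Capture may exist elsewhere.** Neither the eCRF nor the DSMB charter is available. The point is therefore that no such capture is described, not that there is none.

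**Conclusion.** The point holds in a limited form. Serious clinical events attributed to expected IgAN progression can be left out of AE/SAE reporting on one investigator's judgment, without a threshold and without another described route. The three sections that govern this need to be reconciled. The gap lies in hospitalizations, starts of dialysis or transplant, and deaths, and not in renal laboratory values.

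The size cannot be put as a number. A reader might convert the quoted ESRD rates into expected events, but the documents do not support one figure. They give about 30% over 10 years (Protocol 2.1), 30-40% at 20-30 years (2.2), and 5% to 60% over 10 years depending on proteinuria (4.2). Those patients were not selected by this trial's entry criteria, and no rate of hospitalized flares is given.

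Investigators are blinded (6.3), so the filter does not act on known treatment. It can still remove drug-related events that resemble progression. The conclusion assumes that the charter and eCRF add no separate record of these events. If they do, what remains is the wording conflict and the missing SAP table. The primary efficacy analysis is not affected.

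**What to change.** **Protocol.** Revise 10.3.1, 8.3.2 and 10.3.2 together, since deleting the sentence in 10.3.2 alone would leave the other two exclusions in conflict with it. State that death from any cause, hospitalization for any medical reason, and start of dialysis or transplant are recorded in the eCRF whatever the attribution, and are given to the DSMB by arm. Events judged to be expected progression may stay exempt from expedited single-case reporting. Use one test for progression in all three sections.

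**SAP 4.7.** Add one table by arm of these events, including all-cause deaths. Add the number of participants with an eGFR fall of more than 30% sustained for 3 months, computed from scheduled creatinine against the baseline in SAP 3.4. This is a count for analysis only: it borrows the figure in 7.1, does not judge cause or reversibility, and leaves the rule for stopping drug as it is.

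**Cost.** Protocol wording, a few extra forms for events that prove to be natural history, and one table from data already collected. Participants who have already finished would need a query to sites for past hospitalizations and deaths.

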10.3.3 Recording and Follow-Up of Adverse Event and/or Serious Adverse Event

Adverse Event and Serious Adverse Event Recording
 
 • When an AE/SAE occurs, it is the responsibility of the Investigator to review all documentation (eg, hospital progress notes, laboratory reports, diagnostics reports) related to the event. • The Investigator will then record all relevant AE/SAE information in the eCRF. • It is not acceptable for the Investigator to send photocopies of the participant’s medical records in lieu of completion of the AE/SAE CRF page. • There may be instances when copies of medical records for certain cases are requested. In this case, all participant identifiers, with the exception of the participant number, will be redacted on the copies of the medical records before submission. • The Investigator will attempt to establish a diagnosis of the event based on signs, symptoms, and/or other clinical information. Whenever possible, the diagnosis (not the individual signs/symptoms) will be documented as the AE/SAE.

Assessment of Intensity
 
The Investigator will make an assessment of intensity for each AE and SAE reported during the study and assign it to one of the following categories:
 
 • Mild: An event that is easily tolerated by the participant, causing minimal discomfort and not interfering with everyday activities. • Moderate: An event that causes sufficient discomfort and interferes with normal everyday activities. • Severe: An event that prevents normal everyday activities. An AE that is assessed as severe should not be confused with a SAE. Severe is a category utilized for rating the intensity of an event; and both AEs and SAEs can be assessed as severe. 
An event is defined as ‘serious’ when it meets at least one of the predefined outcomes as described in the definition of an SAE, NOT when it is rated as severe.

Assessment of Causality
 
The Investigator is obligated to assess the relationship between study intervention and each occurrence of each AE/SAE. Assessment of causal relationship of an AE to the study intervention is defined as follows:
 
 • Related: There is a reasonable possibility of a temporal and causal relationship between study intervention and the AE.

- **Not Related:** There is no temporal or causal relationship between study intervention and the AE.

The Investigator will use clinical judgment to determine the relationship. Alternative causes, such as underlying disease(s), concomitant therapy, and other risk factors, as well as the temporal relationship of the event to study intervention administration will be considered and investigated. The Investigator will also consult the Investigator’s Brochure (IB) and/or Product Information, for marketed products, in his/her assessment.

For each AE/SAE, the Investigator **must** document in the medical notes that he/she has reviewed the AE/SAE and has provided an assessment of causality. There may be situations in which an SAE has occurred and the Investigator has minimal information to include in the initial report. However, it is very important that the Investigator always make an assessment of causality for every event before the initial transmission of the SAE data.

The Investigator may change his/her opinion of causality in light of follow-up information and send a SAE follow-up report with the updated causality assessment.

The causality assessment is one of the criteria used when determining regulatory reporting requirements.

Follow-up of Adverse Events and Serious Adverse Events

The Investigator is obligated to perform or arrange for the conduct of supplemental measurements and/or evaluations as medically indicated to elucidate the nature and/or causality of the AE or SAE as fully as possible. This may include additional laboratory tests or investigations, histopathological examinations, or consultation with other health care professionals.

New or updated information will be recorded in the originally completed eCRF.

The Investigator will submit any updated SAE data to the Sponsor within 24 hours of receipt of the information.

